### 9.3 Major Secondary Endpoints

Secondary efficacy endpoints include:

- Proportion of subjects with SVR4, SVR18 and SVR24
- Change from baseline in  $\log_{10}$  HCV RNA
- Actual values of  $\log_{10}$  HCV RNA
- Proportion of subjects with on-treatment virologic response at all timepoints (HCV RNA not detected; HCV RNA < LLOQ detected; HCV RNA not detected or HCV RNA < LLOQ detected)
- Proportion of subjects with failure
- Proportion of subjects with on-treatment failure
- Proportion of subjects with viral relapse

#### 9.3.1 Definitions

**SVR4, SVR18 and SVR24** are defined similarly as SVR12 but with 4 weeks, 18 weeks and 24 weeks respectively, instead of 12 weeks.

In addition, for SVR24, the time point of SVR is defined as follows:

- 24 weeks after actual EOT (i.e. the last available measurement in follow up Week 24 analysis window)
- or, if not available, the first measurement available, after the follow-up Week 24 analysis window
- or, if not available, the last measurement available in the SVR18 analysis window, on condition that the time point of SVR24 has been reached

- or, if not available, the last measurement available in the follow up Week 12 analysis window (on condition that the time point of SVR24 has been reached)
- or, if not available, the subject is considered as not having SVR24

For SVR18, the timepoint of SVR is defined as follows:

- 18 weeks after the actual EOT (i.e. the last available measurement in follow up Week 18 analysis window)
- or, if not available, the subject is considered as not having SVR18

**On-Treatment failure** is defined as subjects who did not achieve SVR12 and with confirmed HCV RNA  $\geq$ LLOQ at the actual end of study drug treatment. Includes subjects:

- With viral breakthrough, defined as a confirmed increase of  $>1$  log10 in HCV RNA from nadir, or confirmed HCV RNA of  $>100$  IU/mL in subjects whose HCV RNA had previously been  $<$ LLOQ while on treatment.
- With inadequate virologic response, defined as  $<1$  log10 decline from baseline in HCV RNA after 4 weeks of treatment
- Who do not experience viral breakthrough or inadequate virologic response and have confirmed HCV RNA  $\geq$ LLOQ at the actual end of study drug treatment (e.g., completed study drug treatment, discontinued due to adverse events, withdrawal of consent).

**Viral Relapse** is defined as follows:

Subjects who achieved HCV RNA  $<$ LLOQ at the actual end of study drug treatment and developed HCV RNA  $\geq$ LLOQ during post-treatment follow up.

**Failure (No SVR12):** Subjects who did not achieve SVR12, including:

- On-treatment failure (see above)
- Post-treatment failure, including subjects with:
  - Viral relapse (see above)
  - Missing HCV RNA at time point of SVR12

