5	3	N	800	50 QOD	75	8 (N=5) 12 (N=14)	Through SVR24 Through EOT	0/5 (0%), SVR24 13/14 (93%), EOT
6	1	Y	800	50 QOD	75	8	Enrolling (N=11)	9/10 (90%), SVR12*
7	1	Y	800	25 QD	75	8	Screening/Planned	N/A
8	1	Y	800	25 QD	75	8	Screening/Planned	N/A
9	1	Y	800	25 QD	75	12	Screening/Planned	N/A
10	1	Y	800	25 QD	75	12	Screening/Planned	N/A
11	2	Y	800	25 QD	75	12	Screening/Planned	N/A
12	2	Y	800	25 QD	75	8	Screening/Planned	N/A
12-15	TBD							

* Subject 11 has completed treatment. SVR visit results pending.

[^] N=10-20 per cohort; In ongoing cohorts in which a dosing regimen is modified (e.g. treatment duration is extended) due to apparently insufficient efficacy/safety, the cohort size may be increased such that 20 subjects at the final dosing regimen are enrolled in that cohort.

This protocol permits enrollment of up to 16 cohorts. The maximum permissible enrollment in this study is up to 320 subjects.

Safety and tolerability will be evaluated on an ongoing basis through assessment of AEs, blood and urine sample analyses, collection of ECG, echocardiograms, vital signs and physical examinations. PK data will be routinely reviewed as it becomes available.

[figure not shown]
All enrolled subjects will be monitored from Day 1 through end of follow up for on treatment failure or relapse as defined by the criteria outlined in Sections 8.2.2–8.2.4. The Sponsor will provide the Investigator with the results of the resistance evaluation to enable them to evaluate the most appropriate therapeutic option for any subject that experiences relapse. Where necessary, the Sponsor will offer appropriate retreatment within a separate protocol or, if the subject is unable or unwilling to participate in that trial, the Sponsor will provide reimbursement for locally available HCV treatment for any subjects that experience on treatment failure or relapse, subject to local regulations. Alternatively, where possible, subjects will be allowed to enroll in a subsequent clinical trial subject to meeting the relevant entry criteria.

PK samples will be obtained at a single time point prior to dosing at all routine study visits while subjects are receiving study medication as well as at Weeks 3 and 6, 2-4 hours postdose, and at Weeks 4 and 8, 6-8 hours postdose. In addition, for a subgroup of up to 250 subjects, additional PK samples will be obtained at Week 2 for all treatment groups.

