3.2.2 Secondary Endpoints

- The proportion of subjects who have a sustained virologic response (SVR; i.e., HCV RNA concentration <LLOQ (<15 IU/mL) at 4, 8, 12, 18 and 24 weeks after the last actual dose of treatment
- PK parameters for AL-335 (and metabolites), ODV and SMV in plasma
- The proportion of subjects who experience virologic relapse during the follow-up period.
- The proportion of subjects who have on treatment failure while receiving study

medication

- Viral kinetics, as determined at different timepoints during treatment by the proportion of subjects who achieve
 - HCV RNA <LLOQ Undetectable
 - HCV RNA <LLOQ
- Time to achieve undetectable HCV RNA and <LLOQ HCV RNA
- The amino acid sequence of the NS5A, NS5B and NS3/4A proteins at baseline and post-baseline in subjects who fail treatment
- Effect of various baseline and host disease-related characteristics on treatment outcome

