4.6.2 Procedures for Subjects Who Discontinue Treatment

Subjects who discontinue from treatment should undergo the Study Completion procedures tabulated in Section 6.1 for the purpose of safety monitoring within 7 days after their last dose of study medication. Any subject that discontinues with ongoing AEs should be followed until resolution of their AE(s) or until the investigator has determined that the AE(s) has stabilized. In addition subjects should be followed up per Table 6-4 off treatment for up to 24 weeks, or when commencing therapy if earlier.

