**Otherwise SVR12 is classified as a failure (0).**

\* Confirmed means that the criterion should be fulfilled at 2 or more consecutive time points or at the last observed time point.

Time point of SVR12:

- 12 weeks after the actual EOT (i.e. the last available measurement in the SVR12 analysis window)
- or, if not available, the first available measurement at least 12 weeks after the actual EOT (i.e. the first available measurement after the SVR12 analysis window)
- or, if not available (i.e. no measurement at least 12 weeks after the actual EOT), the subject is considered a failure.

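### SAP 9.3.1 treats a missing HCV RNA sample differently at SVR12, SVR18 and SVR24, so SVR24 can rest on a Week 12 sample and can exceed SVR18

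*SAP*

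**What the plan says.** SAP 9.2.1 scores SVR12 from the latest sample in the Week 12 window, or else from the first sample after it. With neither, the rule is "or, if not available (i.e. no measurement at least 12 weeks after the actual EOT), the subject is considered a failure". An earlier sample is never used.

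SAP 9.3.1 says the other SVR time points follow the SVR12 definition, then gives two of them their own rules:

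- SVR24 looks first in or after the Week 24 window. It then falls back to "the last measurement available in the SVR18 analysis window, on condition that the time point of SVR24 has been reached", and finally to "the last measurement available in the follow up Week 12 analysis window (on condition that the time point of SVR24 has been reached".
- SVR18 looks only in its own window: "or, if not available, the subject is considered as not having SVR18".

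The paragraph on missing and retest values in SAP section 4 says missing data are left alone except for PK values and dates. Protocol 8.2.1 ties each SVR to HCV RNA at the named week and has no carry-forward.

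Three related texts matter. Protocol 4.6.2 places the procedures after early discontinuation "within 7 days after their last dose of study medication", and Protocol Table 6-4 draws HCV RNA at that visit. Protocol 3.2.2 lists SVR "at 4, 8, 12, 18 and 24 weeks after the last actual dose of treatment", whereas SAP 9.3 lists "Proportion of subjects with SVR4, SVR18 and SVR24" beside SVR12. For a subject with on-treatment failure or relapse who cannot or will not join the retreatment protocol, Protocol 2.1 says "the Sponsor will provide reimbursement for locally available HCV treatment".

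**The concern.** SVR24 adds to SVR12 by showing whether response was lost after Week 12. A Week 12 sample cannot show that, yet it may decide SVR24 for exactly those subjects who were not sampled again. The protocol's own background shows that the two can differ. In the study of odalasvir plus ribavirin in genotype 1b (Protocol 1.3.2), six subjects were suppressed at the end of treatment, and 5, 4 and 3 of them achieved SVR4, SVR12 and SVR24. The cause of the later loss is not given.

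SVR18 errs the other way, since a missed Week 18 visit is failure even when Week 24 is clean. The series of SVR rates then mixes virology with different missing-data rules. SVR24 can exceed SVR18 for no virologic reason.

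Two smaller gaps sit beside this. The SVR4 window opens within days of the last dose. And no SVR rule says what happens once a subject starts other HCV therapy.

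**Working it through.** **1. Windows on the scale of days after last dose.** SAP 3.2 ends the treatment phase 3 days after the last intake and starts follow-up the next day. Days after last dose = follow-up day + 3. The SAP's targets agree: follow-up day 25 + 3 = 28.

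| Time point | SAP follow-up days | Days after last dose | Protocol Table 6-4 visit (days) |
|---|---|---|---|
| Week 4 | 1–39 | 4–42 | 21–35 |
| Week 12 | 68–102 | 71–105 | 70–98 |
| Week 18 | 103–144 | 106–147 | 112–140 |
| Week 24 | 145 onward | 148 onward | 154–182 |

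The Week 24 window has no upper end, so the SVR24 step that looks after that window can never apply.

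**2. The rules applied to four sampling patterns.** All four subjects are below LLOQ at Week 12, and the SVR24 condition is taken as met. The last column applies the SVR12 rule throughout.

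| Pattern after Week 12 | SAP: SVR12 / 18 / 24 | SVR12 rule throughout |
|---|---|---|
| A. No further sample | 1 / 0 / 1 | 1 / 0 / 0 |
| B. Week 18 missed, Week 24 below LLOQ | 1 / 0 / 1 | 1 / 1 / 1 |
| C. Week 18 below LLOQ, Week 24 missed | 1 / 1 / 1 | 1 / 1 / 0 |
| D. Relapse seen at Week 18, Week 24 missed | 1 / 0 / 0 | 1 / 0 / 0 |

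A and C raise SVR24 relative to counting missing as failure. B lowers SVR18. D shows that an observed relapse stands, because a Week 18 sample takes precedence over Week 12.

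**3. The plan's own intervals.** Clopper-Pearson limits are the Beta(x, n−x+1) quantile at 0.025 and the Beta(x+1, n−x) quantile at 0.975. For 18/20 this gives 68.3–98.8%, and for 19/20 it gives 75.1–99.9%. Both match Protocol 9.3.

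**4. Size.** The documents give no rate of missed follow-up visits, so k, the number of pattern A subjects, is an assumption. All other subjects respond.

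| n | k | SVR24 under the SAP | SVR18, or SVR24 with missing = failure |
|---|---|---|---|
| 20 | 0 | 100% (83.2–100) | 100% (83.2–100) |
| 20 | 1 | 100% (83.2–100) | 95% (75.1–99.9) |
| 20 | 2 | 100% (83.2–100) | 90% (68.3–98.8) |
| 20 | 3 | 100% (83.2–100) | 85% (62.1–96.8) |
| 10 | 0 | 100% (69.2–100) | 100% (69.2–100) |
| 10 | 1 | 100% (69.2–100) | 90% (55.5–99.7) |
| 10 | 2 | 100% (69.2–100) | 80% (44.4–97.5) |

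Each carried subject is worth 1/20 = 5 points or 1/10 = 10 points.

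**5. SVR4.** The earliest eligible sample is on day 4, which is 21 − 4 = 17 days before the earliest protocol visit. SAP 3.2 uses the last sample in a window, so an early-termination sample from days 4–7 decides SVR4 only if nothing later was drawn through day 42. If that sample is not detected, SAP 9.2.1 makes it a success without looking further.

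**6. Other HCV therapy.** The SAP 9.2.1 algorithm reads the sample at the time point and, in some cases, the next one. It does not ask about treatment in between. A completer who relapses, takes reimbursed local therapy and is below LLOQ in a later window while still followed could be scored a success there.

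**The case against.** A reader might infer that the durability rates are inflated across the board. The documents do not support that. SVR12, which SAP 9.2 names as the primary efficacy endpoint, uses no earlier sample, and SVR18 is conservative. Only SVR24 is raised by the fallback, and only relative to counting missing as failure. It is truly wrong only for a carried subject who relapsed unseen. Observed relapses keep precedence, and relapse is tabulated as its own endpoint.

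A reader might also infer that anyone lost after Week 12 is automatically carried. Both fallbacks require that the SVR24 time point has been reached, which the SAP does not define. If that means the calendar date, a lost subject is carried once the date passes. If it means still being in the study, such a subject is not carried. This limits the claim, but it leaves the derivation to the programmer.

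Nor do the documents show that the SVR24 results in Protocol Table 2-1 (20/20, 18/20, 20/20 and 20/20 in Cohorts 1, 1b, 2 and 3) contain carried subjects. They do not say either way.

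On SVR8, it goes too far to say that the SAP drops it. SAP 3.2 keeps a Follow-up Week 8 window and SAP 9.3.1 still mentions Week 8. What is missing is SVR8 from the 9.3 list and from the Appendix 3 tables. SVR18 is listed but also has no table, so the contradiction might not show in the output.

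It would also be too strong to say that retreated relapsers will count as successes. Protocol 4.6.2 ends follow-up of subjects who discontinued treatment once they start therapy, and 4.6.3 requires withdrawal before entering another investigational-drug study. The gap is left for completers who take local therapy.

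Finally, counting missing as failure mixes dropout with relapse. That is a fair cost, but SVR12 already accepts it. What survives the objection is that the rules contradict each other for the same subject.

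**Conclusion.** The point holds as an inconsistency between missing-sample rules. The same subject can be a failure at Week 18 and a success at Week 24 on a sample taken 71 to 105 days after the last dose. This conflicts with the SAP's statement that these endpoints follow SVR12, with its general missing-data statement, and with the protocol's definition of SVR at the named week. SVR24 can be overstated and SVR18 is biased downward. SVR12 is unaffected by the fallback.

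The size is 5 points per carried subject at n=20 and 10 points at n=10. It rests on an assumed number of missed visits and on reading the SVR24 condition as met. With no carried subjects there is no gap. The SVR4 and other-therapy gaps are real but narrow.

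This should be corrected, but it does not threaten the trial's main conclusions. The primary endpoint is safety, nothing is tested, and the futility criteria in Protocol 4.8.1 use observed virologic failure and relapse rather than derived SVR24.

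**What to change.** In SAP 9.2.1, 9.3 and 9.3.1:

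- Use the SVR12 rule for every SVR time point: last sample in the window, otherwise the first later sample, otherwise failure.
- Keep the carried-forward SVR24 only as a labelled sensitivity analysis. Report the number of subjects carried, and define when the SVR24 time point counts as reached.
- Start the SVR4 window 21 days after the last dose, which is follow-up day 18 (18 + 3 = 21).
- In the analysis, count a subject as not SVR from the start of any other HCV therapy.
- Make the missing-data statement in SAP section 4 refer to these rules.

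Separately, align the endpoint list in SAP 9.3 and the tables in Appendix 3 with the protocol for SVR8 and SVR18.

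The cost is SAP wording and derivation code, with no new data. SVR24 may come out slightly lower and will count dropout as failure, so it should be read beside the relapse table.

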On-treatment Failure	Subjects who did not achieve SVR12 and with confirmed HCV RNA \geq LLOQ at the actual end of study drug treatment. Includes subjects: 
 • With viral breakthrough, defined as a confirmed increase of $>1 \log_{10}$ in HCV RNA from nadir, or confirmed HCV RNA of >100 IU/mL in subjects whose HCV RNA had previously been <LLOQ while on treatment. • With Inadequate virologic response defined as $<1 \log_{10}$ decline from baseline in HCV RNA after 4 weeks of treatment • Who do not experience viral breakthrough or inadequate virologic response and have confirmed HCV RNA \geqLLOQ at the actual end of study drug treatment (e.g., completed study drug treatment, discontinued due to adverse events, withdrawal of consent).
Viral Relapse	Subjects who did not achieve SVR12, with HCV RNA <LLOQ at the actual end of study drug treatment and confirmed HCV RNA \geq LLOQ during follow up.

HCV: hepatitis C virus; LLOQ: lower limit of quantitation; RNA: ribonucleic acid.

Synopsis

A Phase 2a, Open-Label Study to Evaluate the Safety, Pharmacokinetics and Efficacy of the Combination of AL-335 and Odalasvir, with or without Simeprevir, in Treatment-Naïve Subjects with Genotype 1, 2 or 3 Chronic Hepatitis C infection with or without compensated Child Pugh A Cirrhosis

[figure not shown]
Protocol No. :	AL-335-604
Phase:	2a
Study Drugs:	AL-335, Odalasvir (ODV), Simeprevir (SMV)
IND Number:	This is a non-IND study
EudraCT No.:	2016-002845-46
Background Therapy:	None
Comparator:	None
Indication:	Chronic hepatitis C (CHC)

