4.8 Futility Criteria

4.8.1 Predefined Criteria to Determine the Futility of an Individual Treatment Regimen

The futility of any of the regimens evaluated in the study will be assessed by the Sponsor based on predefined criteria, as detailed below. Once a predefined futility criterion is met, appropriate action will be taken by the Sponsor, which may include halting the enrollment of individual treatment arms and/or extending treatment duration of subjects who have not yet reached end of treatment at that time. Futility criteria will be in place during the entire conduct of the study. The Sponsor will evaluate the futility criteria and notify the Principal Investigator if a futility criterion is met.

The objective of the futility criteria is to detect futile regimens as early as possible and ideally within a timeframe that would allow the Sponsor to take action (i.e., while recruitment or treatment phase is ongoing). The futility criteria will take into account post-treatment failure for virologic reasons (viral relapse; see Definitions of Terms). For confirmation of viral relapse, an HCV RNA retest should be scheduled (see Sections 6.2.3 and 6.2.4). However, the Sponsor may evaluate futility criteria based on the original test results without waiting for the retest results.

The futility criteria will have been met:

- If > 2 subjects in any 1 cohort experience viral breakthrough or inadequate virologic response while recruitment is ongoing. Further recruitment in the cohort will then be discontinued
- If $\sim 15\%$ of subjects in a cohort experience relapse at any available timepoint during the follow-up phase (at 24 weeks after actual end of study drug treatment or earlier for subjects who have not yet reached the 24 weeks after actual end of study drug treatment visit).

If the futility criterion is met for a regimen evaluated in a historically easier to treat population (e.g., subjects with GT1 infection without cirrhosis), then that regimen will not be evaluated in historically more difficult to treat populations (e.g., subjects with GT1 infection and with cirrhosis).

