8.2 Efficacy Variables/Measurements

HCV RNA will be measured in all subjects (Section 6.2.3).

The key efficacy variables include the proportion of subjects who achieve SVR demonstrated by sustaining HCV RNA <LLOQ 4, 8, 12, 18 and 24 weeks after the end of treatment (SVR4, SVR8, SVR12, SVR18 and SVR24), regardless of whether or not the subject completed the assigned treatment regimen.

The results will be presented by treatment group by means of descriptive statistics.

The SVR rates will also be presented by subgroups defined by baseline characteristics such as HCV genotype, prior HCV treatment, and IL-28B genotype status.

Additional efficacy variables to be analyzed include:

- The proportion of subjects who have relapse (i.e., who had <LLOQ HCV RNA at actual end of treatment (EOT) followed by \geq LLOQ HCV RNA after planned EOT)
- The proportion of subjects who achieve undetectable HCV RNA <LLOQ (undetectable) at Weeks 2, 4, 6, and 8 after the first dose of study drug
- Time to achieve HCV RNA <LLOQ and <LLOQ undetectable
- The proportion of subjects who have on treatment failure
- The proportion of subjects who achieve SVR12 by IL-28B genotype (CC or non-CC)

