#### 9.2.1 Definition

SVR12 is classified as success or failure according to the following algorithm based on HCV RNA values 12 weeks after the actual end of treatment.

**SVR12 is classified as a success (1) if** at the time point of SVR12, HCV RNA value(s) meet one of the following:

- HCV RNA Not detected or
- < LLOQ detected and
  - the sample is a confirmation\* visit or
  - the sample is the last available HCV RNA measurement or
  - at the next available measurement, HCV RNA not detected or HCV RNA < LLOQ detected
- ≥ LLOQ and
  - the sample is not from a confirmatory visit\* and
  - not the last available measurement in the study and
  - a next measurement is available and HCV RNA not detected or HCV RNA < LLOQ detected for this next measurement

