### 9.3.2 Analysis Methods

The efficacy analysis will be performed on the Safety set and Per Protocol set, by cohort.

Descriptive statistics per cohort and per time point for the continuous parameter (actual values and changes from baseline in  $\log_{10}$  IU/mL HCV RNA) will be calculated.

Tabulations (numbers and proportions) per cohort and per time point for the categorical parameters will be provided. The observed proportion of subjects with SVR4 and SVR24 will be analyzed in the same way as the primary endpoint.

The influence of early virologic response parameters on SVR12 will be explored.

In addition, the reason for failure will be explored by type of failure (see definition of failure above). If more than one type of failure occurs, the order as presented below should be respected:

- a) viral relapse
- b) viral breakthrough
- c) confirmed detected at EOT
- d) missing at time point of SVR

Graphs of individual subject values (spaghetti plots) will be generated for each cohort for the viral load (VL) over time.

Graphs for mean VL change from baseline (+/- SD) over time will be generated for each cohort.

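### Viral relapse has three incompatible definitions, and the SAP's unconfirmed wording can count an SVR12 success as a relapse

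*SAP*

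**What the plan says.** The proportion with viral relapse is a secondary endpoint in Protocol 3.2.2 and 9.2.2 and again in SAP 9.3. It is defined in four places with three different wordings.

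- **Protocol Definitions:** "Subjects who did not achieve SVR12, with HCV RNA <LLOQ at the actual end of study drug treatment and confirmed HCV RNA" at or above LLOQ during follow-up.
- **Protocol 8.2:** below LLOQ at actual EOT, followed by a value at or above "LLOQ HCV RNA after planned EOT".
- **Protocol 8.2.3 and SAP 9.3.1:** below "LLOQ at the actual end of study drug treatment and developed HCV RNA" at or above LLOQ in post-treatment follow-up.

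Three other passages depend on these wordings:

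- **SVR12 (SAP 9.2.1).** A value ≥LLOQ at the SVR12 time point is still a success if it is not from a confirmatory visit, is not the last value, and "a next measurement is available and HCV RNA not detected or HCV RNA < LLOQ detected for this next measurement". Confirmed means met at two or more consecutive time points or at the last observed one.
- **Failure (SAP 9.3.1 and 9.3.2).** The failure group is headed "Subjects who did not achieve SVR12, including", and relapse is listed inside it. The ranked reasons for failure are relapse, breakthrough, "confirmed detected at EOT", and missing at the SVR time point.
- **Futility (Protocol 4.8.1).** One criterion is met if about 15% "of subjects in a cohort experience relapse at any available timepoint during the follow-up phase", up to 24 weeks after treatment. For viral relapse, the section refers to the protocol Definitions.

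**The concern.** The SAP wording lacks two conditions found in the protocol Definitions: confirmation, and absence of SVR12. The same SAP treats relapse as a kind of SVR12 failure, so it contradicts itself. Two programmers working from these texts could produce different relapse tables from the same data.

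The relapse proportion helps describe which regimens and durations hold up, and Protocol 10.8 plans to pool this study's efficacy data with a Phase 2b study to support Phase 3. In cohorts of 10 to 20, one misclassified subject is visible in the result.

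**Working it through.** **1. The three wordings side by side**

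| Source | Counting starts | Confirmation required | No SVR12 required |
|---|---|---|---|
| Protocol Definitions | follow-up | yes | yes |
| Protocol 8.2 | planned EOT | no | no |
| Protocol 8.2.3, SAP 9.3.1 | follow-up | no | no |

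All three require a value below LLOQ at actual EOT.

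**2. HCV RNA patterns traced through the rules.** Each subject is below LLOQ at actual EOT.

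| Pattern | SVR12 (SAP 9.2.1) | Protocol Definitions | SAP 9.3.1 / 9.3.2 |
|---|---|---|---|
| A. One value ≥LLOQ at follow-up Week 12, below LLOQ at Week 18 and after | success | not a relapse | relapse |
| B. One value ≥LLOQ at Week 4, below LLOQ from Week 8 on | success | not a relapse | relapse |
| C. Not detected at Week 12, confirmed ≥LLOQ at Weeks 18 and 24 | success | not a relapse (SVR12 achieved) | relapse |
| D. One value ≥LLOQ at Week 4, below LLOQ at Week 8, then lost | failure | missing | relapse (ranked first) |
| E. Below LLOQ but detected at EOT, no later sample | failure | missing | can fall in category (c) |

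A to C inflate the relapse proportion relative to the protocol Definitions and contradict the SAP's placing of relapse under failure. D and E are failures given a virologic label when the outcome is missing. E arises because SAP 9.3 separates detected below LLOQ from not detected, because the SAP's confirmed includes the last observed time point, and because category (c) says detected where the on-treatment failure definition says ≥LLOQ.

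**3. The plan's own precision figure.** Protocol 9.3 gives a 95% interval of 68.3% to 98.8% for 90% SVR with n=20. The exact Clopper-Pearson interval for 18/20 is 68.3% to 98.8%, so the figure reproduces. It concerns SVR and does not depend on the relapse wording.

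**4. Size of one reclassified subject.** The change is 1/n: 1/20 = 5 points and 1/10 = 10 points. Cohort 1b (Protocol 1.2.1.2) has 2 relapses in 20, or 10.0%; one more would give 3/20 = 15.0%.

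**5. Sensitivity of the reported proportion.** The documents do not give the frequency of values that count only under the SAP wording. Assume a true relapse rate r, and a share b of the remaining subjects with such a value. The expected reported proportion is r + (1 − r)b.

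| r | b = 0 | b = 1% | b = 2% | b = 5% |
|---|---|---|---|---|
| 5% | 5.0% | 5.95% | 6.9% | 9.75% |
| 10% | 10.0% | 10.9% | 11.8% | 14.5% |

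**6. Futility.** Protocol 4.8.1 counts relapse up to 24 weeks after treatment, but the definition it cites excludes anyone who achieved SVR12. Pattern C is therefore inside the rule's time frame and outside its definition. This conflict lies within the protocol.

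**The case against.** The strongest defence is that this is a Phase 2a study with a safety primary endpoint and no hypothesis testing. The SAP repeats Protocol 8.2.3 and does not depart from the protocol as a whole. No transient value is reported: Cohort 1b's 2 relapses match its 18/20 with SVR24. Late relapse is not hidden, because SVR24 has its own table and all HCV RNA values are listed. These points stand, and they limit the severity.

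A reader might infer four stronger claims that the documents do not support.

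- **The SAP wording shifts the 15% futility trigger.** Protocol 4.8.1 refers to the protocol Definitions and separately lets the sponsor act on original results before the retest. SAP section 1 limits the SAP to the final analysis. That one subject can decide a threshold of about 15% is true of any such rule at n=10 to 20.
- **The failure categories will not add up.** SAP 9.3.2 classifies only failures and ranks the reasons, so each receives one label. The exposure is in the relapse proportion and in the labels of patterns D and E, not in the total.
- **Inadequate virologic response drops out.** As defined, on-treatment failure requires confirmed ≥LLOQ at actual EOT, so these subjects would still fall into category (c). Only a sub-label is lost.
- **Protocol 8.2 loses early stoppers who rebound before planned EOT.** Planned treatment lasts at most 12 weeks, and Protocol 4.6.2 provides up to 24 weeks of follow-up off treatment. A sustained rebound would normally still be ≥LLOQ after planned EOT. The gap needs loss to follow-up, new therapy or a transient value.

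**Conclusion.** The inconsistency is real and can be checked from the texts alone. As written, the SAP can count an SVR12 success as a relapse while classing relapse as a form of SVR12 failure. It can also report a subject with a missing outcome as a relapse or as detected at EOT. Each misclassified success adds 5 points (n=20) to 10 points (n=10) to a cohort's relapse rate. Any statement about overall bias rests on an assumed frequency of such values, so none is made here.

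The point should be fixed but is not critical. SVR12, its confidence intervals and the safety primary endpoint do not change. The separate conflict between Protocol 4.8.1 and the protocol Definitions on relapse after SVR12 needs to be resolved within the protocol.

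**What to change.** 1. Use one definition in the protocol Definitions, Protocol 8.2, Protocol 8.2.3 and SAP 9.3.1: below LLOQ at actual EOT, and confirmed ≥LLOQ (two consecutive samples, or the last available) at any time after actual EOT through follow-up Week 24.
2. Report two components separately: relapse without SVR12, which alone belongs under the SAP's No SVR12 heading, and late relapse after SVR12.
3. In SAP 9.3.2, reword category (c) as confirmed ≥LLOQ at EOT, so that a subject last seen detected but below LLOQ is classed as missing. Inadequate virologic response can be shown as an optional sub-label.
4. Reconcile Protocol 4.8.1 with the protocol Definitions by stating whether relapse after SVR12 counts toward futility. Because 4.8.1 relies on those Definitions, step 1 changes what it counts unless this is made explicit. The choice is the sponsor's.

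The cost is wording in two documents. No new data are needed: Protocol 6.2.3 already calls for a retest when HCV RNA reappears, and SAP 9.2.1 already defines confirmed. The changes should be made before database lock.
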